6.4 Details of Laboratory Studies

Testing

Swabs for MRSA:	Patients will have their nares, throat, groin, axilla, and perirectal areas swabbed for MRSA colonization and these swabs will be sent to the microbiology laboratory at the clinical site for determination of the presence of MRSA or MSSA at each of these sites. The laboratory will provide culture results within 3-4 days of swab collection.
Wound and blood cultures:	Patients with an active skin or soft tissue infection will have a culture of the wound performed and sent to the microbiology laboratory of the clinical site for determination of the presence of MRSA or MSSA at each of these sites. Blood cultures may be ordered based on the discretion of the primary physician.
HIV studies:	CD4 count by flow cytometry and HIV viral load will be performed at each clinical site's lab.
Pregnancy test:	Women of childbearing age will have a pregnancy test at baseline to assure she meets inclusion/exclusion criteria. This test will be repeated if she is found to be colonized with MRSA before dispensing the decolonization medications; if she is found to have a positive pregnancy test, her study participation will be terminated.

6.5 Clinical Outcomes

Clinical outcomes as defined by the eradication of MRSA carriage, as well as the incidence of MRSA and soft tissue infections, will be examined and the effect of decolonization procedures for patients carrying MRSA in their nares, throat, groin, axilla, and perirectal areas will be assessed.

6.6 Laboratory Outcomes

The primary and secondary study outcomes involve laboratory data. The measure of the effect of decolonization procedures will include the presence of MRSA on repeated swabs to assess the efficacy of these medications on clearing MRSA colonization. In addition the effect of MRSA infections on the CD4 count and HIV viral load will be assessed.

6.7 Randomization Procedures

Patients who are found to be colonized with MRSA will be randomized to receive either mupirocin (Bactroban®) nasal ointment plus hexachlorophene (pHisoHex®) body washes for seven days or a placebo nasal ointment (white petroleum) and a placebo body soap with no antimicrobial activity for seven days. The patient will be randomized within 7 days of receiving the MRSA positive culture result. Women of childbearing ages will undergo a pregnancy test and those found positive will be terminated from the study. A

randomization list will be generated by a computer program at one controlled location and administered by the Infectious Disease Clinical Research Program (IDCRP), Data Coordination Center (DCC). Assignments will be made at the time that a patient has a positive swab for MRSA colonization. Patients with repeat positive colonization cultures at the 6-month intervals will be re-randomized at these time periods. Enrollment will be stratified by site to ensure an equal number of participants in each study arm per site.

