5.2 Subject Population

The study population will consist of those volunteers from the HIV clinics at the participating military HIV treatment centers including NMCSD, WRNMMC, SAMHS, and NMCP in their respective catchment areas. Each clinic has approximately 500 HIV-positive patients at any one time. Since all adult HIV patients are eligible who do not have allergies to the agents utilized in this study (mupirocin (Bactroban®) nasal ointment or hexachlorophene (pHisoHex®) soaps), who are not healthcare workers with direct patient contact, and who are not pregnant or breastfeeding, over 95% of clinic patients will be eligible for enrollment. A history of prior MRSA colonization and/or infection does not exclude entry into this study. The total population of the study will be 550 participants. If approximately 10-15% of participants carry the bacteria MRSA, then approximately 38 patients will receive topical antibacterial treatment and the other 38 will receive placebo. Enrollment will be on a continuous basis until 550 participants have been enrolled. The number of subjects per site will vary. The San Antonio Military Medical Center will only enroll patients that reside locally to their medical treatment facility. For the retrospective cohort, the study population will consist of all HIV patients who are 18 years or older and followed in the NMCSD HIV clinic.

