Patients who are colonized with MRSA and who reside locally to the medical treatment facility and are able to return to the clinic will have repeat swabs (five swabs from sites listed above) every month (+/- 7 days). A month will be specifically defined as 28 days. Those who have repeat positive colonization swabs during this initial 6 month follow-up period will be observed. This data will assess the efficacy of decolonization procedures on MRSA carriage rates. Patients who are not local to the clinic will not have these repeat swabs performed, but rather will be seen at the next scheduled 6 month study visit. Adherence to the study medications will be assessed at the next scheduled study visit by a patient questionnaire (refer to case report forms). Each time a patient has a positive isolate for MRSA or MSSA, this will be frozen and saved for molecular analysis to determine the most common molecular types colonizing HIV patients and to determine if patients acquire new strains or remain colonized with the same strain over time.

All study patients (both those initially found to be colonized with MRSA and those with negative colonization swabs) will be re-evaluated in six month intervals ($+/- 2$ months) until the end of the study. Patients found to be positive at these subsequent 6 month intervals, will be randomized again, treated and followed as described above. During the last study visit (at the 2-year time period), patients will have swabs, but not undergo randomization. Hence, every 6 months, patients positive during that visit for MRSA colonization will be re-randomized in a 1:1 double-blinded fashion to mupirocin (Bactroban®) nasal ointment twice daily for seven days plus hexachlorophene (pHisoHex®) washes with showering once daily for seven days or to a placebo nasal ointment (white petroleum) and a placebo body soap with no antimicrobial activity for seven days. Repeat randomization will occur every 6 months for those carrying MRSA. For example, some patients initially randomized to receive Bactroban® and pHisoHex®, may later be randomized to the placebo arm, and vice versa.

Begin at the top of diagram again every 6 months ($+/- 2$ months). If patient is found to be positive on swabs, they are re-randomized to one of the two treatment groups for every 6-month positive swab.

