Patients experiencing an infection will be offered decolonization medications based on their most recent randomization assignment; those previously randomized will be maintained in their group, while those experiencing a soft tissue infection and having a positive colonization culture for the first time will be randomized to either mupirocin (Bactroban®) nasal ointment twice daily for seven days and hexachlorophene (pHisoHex®) washes with showering once daily for seven days or to a placebo nasal ointment (white petroleum) and a placebo soap with no antimicrobial activity for seven days. Patients with a positive soft tissue culture but no positive swabs from the nares, throat, groin, axilla, or perirectal areas, will not be randomized. If the primary clinician caring for a patient who experienced a MRSA infection desires to decolonize a patient regardless of the patient's randomization group, this is permitted, but must be documented and these participants will be removed from the "placebo group" for the analysis.

All cultures (from colonization sampling, wound and blood cultures) which are positive for MRSA or MSSA at the local medical treatment facilities laboratories will be preserved by freezing the isolates at -70 degrees C; these samples will be batched (isolates will be held at the primary facility and sent on a periodic basis) and sent overnight with dry ice to the NMCSD. This site will collect the specimens and send them to the laboratory at SAMMC which will perform testing on the isolates for confirmation of MRSA, antibiotic susceptibility testing (including mupirocin), and molecular analysis (to include multilocus sequence testing, PVL PCR, and other virulence factors). Some local laboratories (e.g. NMCSD) are also performing susceptibility testing on the isolates; this information will be collected if available. SAMMC will also repeat all susceptibility testing on all isolates at their facility. All samples sent to the laboratory at SAMMC will be labeled only with a PIN number of the patient. The staff at the SAMMC laboratory will not have access to personal identifiers and will have no way of linking their results to a patient name. Results

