6.10 Termination

A subject's participation will be terminated if one of the following occurs:

- a. Subject voluntarily withdraws
- b. Subject fails to comply with study procedures
- c. Decision in the best interest of the patient
- d. Patient is no longer eligible for care at the military HIV clinics
- e. Patient becomes pregnant or decides to become pregnant during the two-year study period

- f. The patient begins employment as a healthcare worker with direct patient contact

A subject who develops a rash or significant adverse event due to study medication will be discontinued from treatment but will be encouraged to continue to undergo follow up including study visits for completing questionnaires and swabs for MRSA colonization every 6 months (+/- 2 months) until study completion; the patient will not be randomized to one of the treatment arms if he/she is found to be positive again for MRSA colonization. The subject may be withdrawn from the study if it is felt by the clinical investigators that the subject is at an undue risk from further participation.

The subject will require a termination visit if withdrawn from the study. If a subject's participation in this study is terminated, they will be offered medical standard of care and a medical evaluation, to include clinical laboratory studies as needed. The investigator will complete the Completion/Discontinuation CRF.

VII. STATISTICAL ANALYSES

There are four primary questions to be answered to address this study's primary objective. These, and an analysis designed to answer the question, follow.

- (1) What is the hexachlorophene/mupirocin treatment effect to clear MRSA colonization compared to placebo? We will also examine if these decolonization procedures are effective at reducing MRSA infections and skin/soft tissue infections compared to placebo. We propose to pool the data at 6, 12, 18, and 24 months as if they were independent and conduct a chi-square or Fisher's exact test of contingency. These analyses will be conducted for colonization and infection separately. The proposed pooling of this study design assumes that there is no persistent or repeated-treatment effect and that there is no patient-to-patient difference in susceptibility. These effects will be investigated in the following questions.

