Hence to show a statistically significant decline in colonization rates using mupirocin (Bactroban®) and hexachlorophene (pHisoHex®), up to 420 patients would be required. Given potential lost to follow-up events and that the colonization rate or clearance rates may vary, we propose to enroll 550 participants, such that 500 participants are followed throughout the study period. Given this sample size and the estimate of a 10% colonization rate over the study period, we would estimate that 50-55 participants will be randomized. Since participants with repeat colonization events may differ from those with first time MRSA colonization and may differ in response to decolonization medications, we will also examine as a secondary analysis of the primary endpoint only those with unique randomizations.

For showing a significant difference in the number of infections between the two treatment groups, assuming 38% of the no specific treatment group and 10% of the treatment group will develop infection, a sample size of 860 would be needed; of note, this is a secondary objective and not the primary basis of the sample size calculation for this study. For smaller changes in the difference in the rates between groups, larger sample size would be needed. Of note, the first rates (38% vs. 10%) were determined during an 8-10 week period and our study involves 6-month periods over a total two year period; on the other hand, this military training population studied for these estimates may have a higher rate than our HIV patients.

Infection Rate in Treated Group	Infection Rate in Placebo Group	Difference in Infection Rate Between Groups	Power	Alpha level	Total sample size for one time period	Total sample size for every 6 month evaluations
10%	38%	28%	.80	.05	860	277
10%	30%	20%	.80	.05	1440	464
10%	25%	15%	.80	.05	2260	729
5%	15%	10%	.80	.05	3200	1032

To account for the study design of patients being re-examined every 6 months over a two-year period (a total of five visits) and re-randomized at each of these intervals with new infections being counted as separate events, the sample size required was notably smaller (last column in table). The calculations accounted for a progressive decrease in colonization and infection rates over the course of the study since patients would be given decolonization medications depending on their randomization assignment.

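### Randomization is stratified by site but the primary test ignores site; naming one site-stratified test is a minor, nearly free improvement

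*Combined protocol and SAP*

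**What the plan says.** Section 6.7 (Randomization Procedures) has a central list and states: "Enrollment will be stratified by site to ensure an equal number of participants in each study arm per site".

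Section VII, question (1), pools the 6-, 12-, 18- and 24-month data "as if they were independent and conduct a chi-square or Fisher's exact test of contingency". It gives the assumptions behind the pooling, among them that "there is no patient-to-patient difference in susceptibility". No analysis in section VII has a site term, and the choice between the two tests is left open.

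A patient can contribute more than once. Section 6.3 says "Repeat randomization will occur every 6 months for those carrying MRSA", while at infection visits "those previously randomized will be maintained in their group". The analysis restricted to each patient's first randomization is only a sub-analysis (sections 3.1 and VII).

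On numbers, section VII says "we would estimate that 50-55 participants will be randomized"; section 5.2 says "approximately 38 patients will receive topical antibacterial treatment and the other 38 will receive placebo", which is 76. Section VII also sets a goal of at least 50 randomizations and, separately, at least 50 subjects with 6-month data.

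**The concern.** When allocation is balanced within site, differences between sites cannot contribute to the difference between arms. An unstratified test still counts them in its variance. If culture-positive rates differ between sites, that variance is too large, the true type I error drops below 5%, and some power is lost.

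There is reason to think sites might differ. Each site's own laboratory determines colonization (sections 6.4 and 10.1). Central confirmation covers only isolates already positive locally, so it cannot correct differences in local detection. One centre enrols only local residents (section 5.2), and monthly swabs are done only for local patients (section 6.3). None of this gives the size of a site effect.

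At stake is whether the primary p-value and interval match the design, in a comparison with few patients.

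**Working it through.** **1. The plan's own sample size.** Inputs from section VII: 85% of placebo patients remain colonized, against 7%, 23% or 39% of treated patients; power 0.80; alpha 0.05 (sidedness not stated, taken as two-sided); 10% of enrollees colonized. With d = p1 - p2 and p̄ = (p1 + p2)/2:

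- n = [1.96 √(2p̄(1-p̄)) + 0.84 √(p1(1-p1) + p2(1-p2))]² / d²
- continuity-corrected n' = (n/4)[1 + √(1 + 4/(nd))]²

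| Treated rate | n | n' | Rounded up | ÷ 0.10 | Plan, per group |
|---|---|---|---|---|---|
| 0.07 | 5.04 | 7.38 | 8 | 80 | 80 |
| 0.23 | 8.86 | 11.87 | 12 | 120 | 120 |
| 0.39 | 16.25 | 20.36 | 21 | 210 | 210 |

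The match is exact, so the plan already allows for conservatism of the Fisher type. It needs at most 21 colonized patients per arm and expects about 25 to 27. Uncorrected power at 25 per arm for 85% v 39% is 94.3%.

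**2. Why the cost depends on site.** With equal arms within each site, both tests use the same numerator, the difference in positives between arms. They differ in variance. The unstratified test uses p̄(1-p̄), which equals the average within-site p(1-p) plus the variance of p between sites. The stratified test uses, for site k with n_k patients and t_k positives, Σ t_k(n_k - t_k)/[4(n_k - 1)]. If sites do not differ, the extra term is zero and so is the conservatism.

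**3. Simulation.** 40,000 trials per setting, 26 per arm, four sites (9/7/5/5 per arm), balanced within site, site effects normal on the logit scale, one record per patient, overall arm-level rates held at the stated values. Site sizes and standard deviations (SDs) are assumptions.

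| Site SD | Power, 85% v 39%: chi-square | Stratified | Change | Gain, 70% v 35% |
|---|---|---|---|---|
| 0 | 95.5% | 94.9% | -0.6 | about 0 |
| 0.5 | 95.9% | 95.8% | -0.1 | about 1.5 |
| 1.0 | 95.9% | 96.9% | +1.0 | about 5 |
| 1.5 | 95.2% | 97.7% | +2.5 | about 8 to 9 |

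At 85% v 23%, both tests exceed 99%. The largest loss seen from stratifying with no site effect was about 2 points (69.3% v 67.5% at 85% v 55%).

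Type I error over null rates of 50% to 85%: stratified about 4.3-5.4% in every setting. Chi-square was about 4.3-5.6% at SD 0 to 0.5, and from about 4.4% down to 2.8% at SD 1.0 to 1.5. The chi-square figure also moves with the exact counts: at 25 per arm, a 50% null rate and no site effect it was 6.6%, against 5.2% stratified.

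**4. Fisher's test.** At 25 per arm its type I error was 1.4-3.5%. A continuity-corrected stratified test was similarly low (1.3-2.5%), so Fisher's low error comes mainly from small counts, not from omitting site. At 85% v 39% with no site effect its power was 90.9%, against 94.9% for the chi-square.

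**5. The pooled test as written.** Steps 3 and 4 use one record per patient; the planned test does not. With an assumed 50 patients, up to four periods each, a null rate near 0.7 and no site effect (about 126-136 observations), type I error was 4.8-5.3% when arm is re-randomized each period. When arm is kept it was 5.4% if patients do not differ, and 6.8% and 7.9% at patient-level SDs of 1 and 2.

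**The case against.** The best defence is that an unstratified test remains usable here and costs almost nothing at the planned effects. That stands: at 85% v 39% the difference is within about 2.5 points even at a large site SD, and with no site effect the stratified test is slightly weaker. The sample size also carries a continuity correction and some margin.

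A reader might infer that ignoring site makes the primary test conservative outright. The documents do not support that: they give no site rates, and at SD 0 to 0.5 the chi-square sits near 5%.

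A reader might also infer a sizeable power loss. Simulated power of 88.7% v 91.1% (SD 1.0) or 79.3% v 86.2% (SD 1.5) can be produced by treating 85% and 39% as the rates at a typical site and then adding site variation. The overall rates then shrink to about 81% v 41% and 78% v 42%. Section VII states arm-level rates, so these are not power at the planned rates; most of the drop comes from the smaller effect.

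Finally, the pooling of repeat randomizations matters more than the missing site term and can push the error the other way. That is fair. The 6.8-7.9% figures assume the arm is carried throughout, whereas section 6.3 re-randomizes at scheduled visits and keeps the arm only at infection visits, so they are an extreme case.

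**Conclusion.** The mismatch is certain: site is used in the randomization and absent from the primary analysis. Its effect is minor. At the smallest planned effect, stratifying moves power by about -1 to +2.5 points around 95%. A gain of 5 points or more needs both a smaller effect than planned and a strong site effect. The steadier benefit is in type I error, 4.3-5.4% against 2.8-5.6%.

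These figures rest on assumed site sizes and site SDs, about 26 patients per arm, and one record per patient. The number of strata is itself unclear (four centres named in section 5.2, five sites in section XIII); runs with five sites gave the same picture. A case for changing the plan should rest on matching analysis to design and naming one test, not on a claim of serious power loss.

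**What to change.** In section VII, question (1), name one primary test in advance: a site-stratified Cochran-Mantel-Haenszel test, with a Mantel-Haenszel risk difference and confidence interval, on one record per patient. If repeat randomizations are pooled, use instead a logistic model with arm and site and standard errors clustered on patient. Fix a rule for merging very small sites before unblinding. Reconcile the expected number randomized (50-55 or 76) and say whether the target of 50 counts randomizations or subjects.

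The cost is a sentence or two of text. Site is already known for every patient through the site-specific study number (section IX). The statistical downside is a loss of up to about 2 points of power if site has no effect.

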6.8 Study Drug

Mupirocin (Bactroban®) 2% nasal ointment and hexachlorophene (pHisoHex®) 3% soap will be obtained through the pharmacy at the NMCSD. In addition, we will obtain white petroleum as a placebo nasal ointment and a body soap without antibacterial activity as a placebo. Upon receipt of these medications, the pharmacist at the NMCSD will initiate a drug accountability log entitled Investigational Agent Accountability Record. This record will be maintained as a perpetual inventory of both mupirocin (Bactroban®) and hexachlorophene (pHisoHex®).

Once obtained from the NMCSD pharmacy, mupirocin (Bactroban®) nasal ointment, hexachlorophene (pHisoHex®) soap, and the placebo ointment and soap will be provided to each site following a written request via the Clinical Drug Request Form, written confirmation of protocol approval from the IRB of the site requesting the drug, and a copy of the current Randomization Assignment List (if requesting additional drug). The Clinical Drug Request Form and Randomization Assignment List (if applicable) will be faxed to the NMCSD pharmacist each time the drug is requested. Once the above documentation is obtained, the NMCSD pharmacist will send the requested amount of these medications to the pharmacist at the requesting site. The shipment will contain an Investigational Drug Shipment Form (Shipping Manifest Form), which must be faxed to the NMCSD pharmacist following receipt of each medication shipment. In addition, the drug shipment will contain a Study Agent Accountability Log and a Randomization Assignment List. As each site differs in policy with regard to handling investigational medications, the Site Principal Investigator and pharmacist at each site will be accountable for maintaining the Study Agent Accountability Log and the Randomization Assignment List as well as following site-specific procedures of drug accountability, storage and dispensing.

